6.2 Analysis of secondary objectives

The secondary objectives of this study are: safety, tolerability, pharmacokinetics (PK) and anti-tumour activity of VAL201.

6.2.1 Assessment of the safety and tolerability

The assessment of safety and tolerability will be based on the safety data set; the evaluation of AEs will be carried throughout every cycle including follow up period, which is defined as final study visit performed 30 +/- 5 days after last dose of VAL201.

Frequencies and percentages of patients experiencing one or more AEs will be summarized and listed by:

- Dose level where applicable.
- Relationship to the study drug.
- Severity.

Severe Adverse Events (SAEs) and DLTs will be presented separately.

The number of AEs leading to death and treatment emergent AE (TEAE) will be summarised by descriptive statistics. AEs will be coded using the MedDRA dictionary (version 17.0). The SOCs and PTs will be used for tabulation. The number and the percentage of patients with at least one AE will be presented by SOC and PT.

Safety parameters such as vital signs will be listed and summarized as described in section 5.10 of this SAP. Laboratory parameters such as haematology, coagulation, clinical chemistry and urinalysis data will be listed and summarised as indicated in section 5.11 of this SAP. Physical examination and ECG parameters will be listed as indicated in section 5.8 and 5.10 respectively of this SAP.

6.2.2 Evaluation of the pharmacokinetics parameters

The following PK parameters will be derived for each subject from the individual plasma concentration versus time profiles of VAL201: Tmax, Cmax, t(1/2), AUC(0-t), AUC (0-inf), AUMC (0-t), lambda, Cl/F, Vz/F.

All PK variables (except for T_{max}) will be listed.

Patient profile treatment concentrations will be produced (one figure with each individual patient included in the PK population).

A plot of the mean profile of treatment concentration (One figure with means Concentration-Time Curve on a Linear Scale with SD) will also be produced.

6.2.3 Evaluation of anti-tumour activity of VAL201

For patients with prostate cancer or other tumour types where applicable, response rate (assessed by PCWG2 for prostate cancer or RECIST 1.1 for other tumour types), was planned to include CT (or MRI), radionuclide bone scan, and PSA at the selected dose level and assessed in a 2 stage analysis

Forms				
Title		Statistical Analysis Plan Template		
Code		Version	Effective Date	Page
FRM_ST03_032		01	23 Apr 2015	21 of 24

(dose escalation and enrichment respectively). Stage 2 was not reached within the study and only prostate cancer patients were finally included in the trial, so response rate will be summarized for Dose Escalation Stage only, based on responder definition reported in section 4.5; exact 95% CI will be calculated. Prostate Specific Antigen assessment will be summarized as indicated in section 5.12 of this SAP.

6.3 Analysis of exploratory objectives

The planned exploratory objectives of this study were: pharmacodynamics (PD) activity of VAL201 and assessment of tumour biomarkers. Due to the early termination of the study, the related exploratory endpoints will not be analyzed. PSA, LH and Testosterone only, will be included as part of the descriptive analysis for laboratory biochemistry (see section 6.2.1).

7. Tables, Figures and Listings

7.1 Tables

Tables will be provided for the display of data from this study and are numbered following the ICH E3 “Structure and Content of Clinical Study Report”.

All tables will be presented in landscape format.

The standard font size is 9 points Courier New for all tables.

Titles will be center-aligned; footnotes will be left-aligned.

Each table will have 2 titles:

- The 1st title will be the table/figure number with the description of the table;
- The 2nd title will be a description of the study population presented in the table.

Some tables will have a third title (before 2nd title) with a description of the statistical method used in those tables.

Any footnote added to explain the table contents will be presented in the following format:

Note 1: Percentages are calculated on the number of patients (N).

Note 2: A serious adverse event is an

Note 3:

The last two footnotes of each table will be footers indicating:

- the reference listing of the data;
- the program name, the date and time of generation and the SAS[®] version used.

7.2 Tables listings and figures

7.2.1 Tables:

 cros nt	Forms			
	Title	Statistical Analysis Plan Template		
	Code	Version	Effective Date	Page
	FRM_ST03_032	01	23 Apr 2015	22 of 24

TABLE 14.1-1	DISPOSITION OF PATIENTS / SUMMARY OF ALL PATIENTS AND ANALYSIS SET
TABLE 14.1-2.1	SUMMARY OF MAJOR PROTOCOL DEVIATION / INTENT TO TREAT POPULATION
TABLE 14.1-2.2	SUMMARY OF MINOR PROTOCOL DEVIATION / INTENT TO TREAT POPULATION
TABLE 14.1-3.1	DEMOGRAPHIC CHARACTERISTIC / INTENT TO TREAT POPULATION
TABLE 14.1-4	SUMMARY OF TUMOUR ASSESSMENT / INTENT TO TREAT POPULATION
TABLE 14.1-5.1	MEDICAL HISTORY BY SYSTEM ORGAN CLASS AND PREFERRED TERM / INTENT TO TREAT POPULATION
TABLE 14.1-5.2	CONCOMITANT DISEASE BY SYSTEM ORGAN CLASS AND PREFERRED TERM / INTENT TO TREAT POPULATION
TABLE 14.1-6.1	PREVIOUS MEDICATIONS / INTENT TO TREAT POPULATION
TABLE 14.1-6.2	CONCOMITANT MEDICATIONS / INTENT TO TREAT POPULATION
TABLE 14.2-1	SUMMARY OF DOSE LIMITING TOXICITY (DLT) BY COHORT / SAFETY POPULATION
TABLE 14.2-3.1	PROSTATE SPECIFIC ANTIGEN (PSA) ASSESSMENT / INTENT TO TREAT POPULATION
TABLE 14.2-3.2	PROSTATE SPECIFIC ANTIGEN (PSA) ASSESSMENT / PER PROTOCOL POPULATION
TABLE T14.2-4.1	SUMMARY OF RESPONSE RATE ANTI TUMOUR ACTIVITY / INENT TO TREAT POPULATION
TABLE T14.2-4.2	SUMMARY OF RESPONSE RATE ANTI TUMOUR ACTIVITY / PER PROTOCOL POPULATION
TABLE T14.3.1-1.1	SUMMARY OF TREATMENT-EMERGENT ADVERSE EVENTS BY DOSE/ DOSE ESCALATION SAFETY POPULATION
TABLE T14.3.1-2.1	SUMMARY OF TREATMENT EMERGENT ADVERSE EVENT BY SYSTEM ORGAN CLASS AND BY DOSE / DOSE ESCALATION SAFETY POPULATION
TABLE T14.3.1-3.1	SUMMARY OF TREATMENT EMERGENT ADVERSE EVENT BY SYSTEM ORGAN CLASS AND BY SEVERITY / DOSE ESCALATION SAFETY POPULATION
TABLE T14.3.1-4.1	SUMMARY OF TREATMENT EMERGENT ADVERSE EVENT BY SYSTEM ORGAN CLASS AND BY CAUSALITY / DOSE ESCALATION SAFETY POPULATION
TABLE 14.3.4-1.1	ESTERN CO-OPERATIVE ONCOLOGY GROUP (ECOG) PERFORMANCE STATUS / INTENT TO TREAT POPULATION
TABLE 14.3.4-1.2	ESTERN CO-OPERATIVE ONCOLOGY GROUP (ECOG) PERFORMANCE STATUS / PER PROTOCOL POPULATION
TABLE 14.3.4-2.1	SUMMARY VITAL SIGNS BY CYCLE AND VISIT / INTENT TO TREAT POPULATION

 cros nt	Forms			
	Title	Statistical Analysis Plan Template		
	Code	Version	Effective Date	Page
	FRM_ST03_032	01	23 Apr 2015	23 of 24

TABLE 14.3.4-2.2	SUMMARY VITAL SIGNS BY CYCLE AND VISIT / PER PROTOCOL POPULATION
TABLE 14.3.4-3.1.1	LABORATORY PARAMETERS: CLINICAL CHEMISTRY BY CYCLE AND TIME POINTS / INTENT TO TREAT POPULATION
TABLE 14.3.4-3.1.2	LABORATORY PARAMETERS: HAEMATOLOGY AND COAGULATION BY CYCLE AND TIME POINTS / INTENT TO TREAT POPULATION
TABLE 14.3.4-3.1.3	LABORATORY PARAMETERS: URINALYSIS BY CYCLE AND TIME POINTS / INTENT TO TREAT POPULATION
TABLE 14.3.4-3.2.1	LABORATORY PARAMETERS: CLINICAL CHEMISTRY BY CYCLE AND TIME POINTS / PER PROTOCOL POPULATION
TABLE 14.3.4-3.2.2	LABORATORY PARAMETERS: HAEMATOLOGY AND COAGULATION BY CYCLE AND TIME POINTS / PER PROTOCOL POPULATION
TABLE 14.3.4-3.2.3	LABORATORY PARAMETERS: URINALYSIS BY CYCLE AND TIME POINTS / PER PROTOCOL POPULATION

7.2.2 Listings:

LISTING 16.2.1-1	DISPOSITION OF PATIENTS / ALL PATIENTS
LISTING 16.2.2-1	PROTOCOL DEVIATIONS / INTENT TO TREAT POPULATION
LISTING 16.2.3-1	DEMOGRAPHIC AND BASELINE CHARACTERISTICS / INTENT TO TREAT POPULATION
LISTING 16.2.4-1	PHYSICAL EXAMINATIONS / INTENT TO TREAT POPULATION
LISTING 16.2.4-2	PAST-CONCOMITANT DISEASES / INTENT TO TREAT POPULATION
LISTING 16.2.4-3	STUDY CANCER HISTORY / INTENT TO TREAT POPULATION
LISTING 16.2.4-4	TUMOUR ASSESSMENT / INTENT TO TREAT POPULATION
LISTING 16.2.5-1	MEDICATIONS / INTENT TO TREAT POPULATION
LISTING 16.2.6-1	PROSTATE SPECIFIC ANTIGEN (PSA) / INTENT TO TREAT POPULATION
LISTING 16.2.6-2	OTHER SOLID TUMOUR / INTENT TO TREAT POPULATION
LISTING 16.2.7-1	PRE-TREATMENT ADVERSE EVENTS / INTENT TO TREAT POPULATION
LISTING 16.2.7-2.1	TREATMENT-EMERGENT ADVERSE EVENTS / SAFETY POPULATION
LISTING 16.2.7-2.2	SERIOUS TREATMENT-EMERGENT ADVERSE EVENTS / SAFETY POPULATION
LISTING 16.2.7-2.3	TREATMENT-EMERGENT ADVERSE DRUG REACTIONS / SAFETY POPULATION
LISTING 16.2.7-2.4	TREATMENT-EMERGENT ADVERSE EVENTS LEADING TO DISCONTINUATION / SAFETY POPULATION
LISTING 16.2.7-2.5	TREATMENT-EMERGENT ADVERSE EVENTS AS CODED / SAFETY POPULATION

Forms				
Title		Statistical Analysis Plan Template		
Code		Version	Effective Date	Page
FRM_ST03_032		01	23 Apr 2015	24 of 24

LISTING 16.2.8-1	VITAL SIGNS / INTENT TO TREAT POPULATION
LISTING 16.2.8-2	12-LEAD ECG / INTENT TO TREAT POPULATION
LISTING 16.2.8-3	ESTERN CO-OPERATIVE ONCOLOGY GROUP (ECOG) PERFORMANCE STATUS / INTENT TO TREAT POPULATION
LISTING 16.2.8-4.1	LABORATORY PARAMETERS: CLINICAL CHEMISTRY / INTENT TO TREAT POPULATION
LISTING 16.2.8-4.2	LABORATORY PARAMETERS: HEAMATOLOGY AND COAGULATION / INTENT TO TREAT POPULATION
LISTING 16.2.8-4.3	LABORATORY PARAMETERS: URINALYSIS / INTENT TO TREAT POPULATION
LISTING 16.2.8-6	PK PARAMETERS / PK POPULATION

7.2.3 Figures:

FIGURE F14.2-1.1	PATIENT PROFILE OF TREATMENTS CONCENTRATIONS / PK POPULATION
FIGURE F14.2-1.2	MEAN PROFILE OF TREATMENTS CONCENTRATIONS / PK POPULATION

8. Appendices

See document “Val201-001_SAP_Appendix_Amendment _3.0.docx”.

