3.1 General design and plan

This clinical study is designed to establish the MTD/MAD, safety, tolerability and PK of VAL201 by testing the drug (VAL201) on patients with incurable, locally advanced or metastatic prostate cancer and other advanced solid tumors. The design is a Phase I/II, open-label single-arm dose escalation study. The study design consists of a dose escalation part followed by an enrichment part. The study features includes: five cohorts of up to six patients, six cycles (main study) each cycle will last 21 days and an extended treatment period of VAL201 if a patient is considered suitable. Events that occur during each cycle will be considered for Dose Limiting Toxicity (DLT) assessment and therefore to establish the MTD/MAD.

The dose escalation will follow an accelerated enrolment of 3+3 design where the first two cohorts will enroll 1 patient each with an accelerated dose escalation schedule as described on Section 4.2 of the clinical study protocol (VAL201-001 version F6.0). Each patient will be followed up for AEs and DLT during each cycle. Where the Cohort Review Committee (CRC) suspects that drug-related events have occurred that merit further exploration at that dose level, they will request that the cohort 1 or 2 must enroll 3 more patients in order to thoroughly evaluate safety events prior to escalation. Cohorts of 3 patients will be enrolled from the 3rd cohort onwards (or earlier where the CRC recommend due to safety data evaluation). After a DLT has been identified the cohort will be expanded to 6 patients. If a second DLT is reported this will be declared the MTD.

The starting dose of VAL201 for the first cohort of patients will be 0.5 mg/kg/dose given on Days 1, 8 and 15 of each cycle. In the absence of DLT, the dose of VAL201 will be escalated for future cohorts in recommended increments according to the rules for dose escalation as described in Section 4.2 of clinical study protocol. All dose escalation decisions will be made by a CRC who shall convene to review all available safety data.

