3.3 Sample size justification

Up to 42 patients with incurable, locally advanced or metastatic prostate cancer or other advanced solid tumours may be enrolled in this study. It will follow a dose escalation design, and the number of patients treated will therefore be dependent upon the number of dose levels investigated. A conventional algorithm (3+3 patients per dose level) will be used to identify the MTD or MAD, escalating on 0/3 or 1/6 DLTs, and de-escalating if 2 or more patients with DLTs are encountered. The MTD will be the highest dose level at which 0 of 3 or 1 of 6 patients experience a DLT, with the next higher dose having at least 2 of 3 or 2 of 6 patients experiencing a DLT.

The following table shows the operating characteristics of this 3+3 design. Under this design, there is a 71% chance of escalation if the true but unknown rate of DLT is 20% and less than 50% chance of escalation if the true but unknown rate of DLT is higher than 30%.

Operating characteristics of the 3+3 study design

True but Unknown Rate of DLT (%)	Probability of Escalation (%)
20	71
30	49
40	31
50	17
60	8

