6.1 Analysis of primary objective

The primary objective of this study is to estimate the MTD/MAD of VAL201 throughout an accelerated dose escalation design (3+3 patients per dose level). The first 2 cohorts will enroll 1 patient only (see Section 1.5 of the study protocol). For each cohort, patients will be followed up for adverse events (AEs) and DLT during each cycle.

The escalating dose will be determined if 0 patients out of 3 or 1 patient out of 6 experience a DLT, and de-escalating if 2 or more patients with DLTs are encountered. Therefore the MTD will be the highest dose level at which 0 of 3 or 1 of 6 patients experience a DLT.

The CRC will review all patient safety data at the end of Cycle 1 and only permit dose escalation to the next dose level where there are no safety concerns. Where the CRC suspects that drug-related events have occurred that merit further exploration at that dose level, they will request that Cohort 1 or 2 must enroll 3 more patients in order to more thoroughly evaluate safety events prior to escalation. Cohorts of 3 patients will be enrolled from the 3rd cohort onwards (or earlier where the CRC recommend due to safety data evaluation) thereafter the cohort will be expanded to 6 patients upon identification of a DLT. If a second DLT is reported this will be declared the MTD.

There will be no formal statistical analysis in the dose-escalation phase. However, safety data such as AEs and DLT will be listed and summarised by dose level separately using descriptive statistics. Pre-treatment AEs will be listed.

Forms				
Title		Statistical Analysis Plan Template		
Code		Version	Effective Date	Page
FRM_ST03_032		01	23 Apr 2015	20 of 24

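### The MTD is defined by DLT counts per dose level, but the only DLT table is titled by cohort and Cohort 5 can span two dose levels; the modal-dose rule in SAP 4.1 adds a narrower attribution gap

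*SAP*

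**What the plan says.** **Definition of the MTD.** SAP 3.3 states: "The MTD will be the highest dose level at which 0 of 3 or 1 of 6 patients experience a DLT, with the next" higher level showing at least 2 of 3 or 2 of 6. SAP 6.1 repeats the first half: "Therefore the MTD will be the highest dose level at which 0 of 3 or 1 of 6 patients experience a DLT".

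**Promised display.** SAP 6.1 says that "safety data such as AEs and DLT will be listed and summarised by dose level separately using descriptive statistics". SAP 6.2.1 adds: "Severe Adverse Events (SAEs) and DLTs will be presented separately".

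**Listed display.** The one DLT table in SAP 7.2.1, Table 14.2-1, is titled "SUMMARY OF DOSE LIMITING TOXICITY (DLT) BY COHORT / SAFETY POPULATION". In the same list, Tables T14.3.1-1.1 and T14.3.1-2.1 (treatment-emergent adverse events) are titled by dose. None of the 23 listing titles in 7.2.2 names DLTs.

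**Cohort and dose.** Under SAP 3.1, Cohort 5 is dosed at 8 mg/kg in Cycle 1, and the review committee may approve 16 mg/kg from Cycle 4 Day 1. Doses may be reduced after a DLT at either level. SAP 4.6 records that DLTs are now followed in every cycle, not only the first.

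**Dose group for analysis.** SAP 4.1 bases efficacy and safety analyses on the treatment actually received, because the committee may adjust individual doses. It then assigns each subject to the dose taken most often in each cycle. The stated purpose is to absorb occasional dosing errors.

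**The concern.** The primary objective is the MTD/MAD, and the quantity that decides it is a count of DLT patients at a dose level. Where every patient in a cohort stays on one dose, a table by cohort supplies that count. In Cohort 5 it need not: DLTs before and after the dose change can fall in one row. As titled, the only table for the primary objective is therefore not stated to show the number that 3.3 and 6.1 ask for.

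A second, smaller matter concerns the by-dose adverse event tables. If the modal rule is applied literally to a cycle in which the dose was cut because of toxicity, the event that prompted the cut can be tabulated under the lower dose. That would understate toxicity at the higher dose and overstate it at the lower one.

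**Working it through.** **The plan's own figure.** The 3.3 table follows from P(escalate) = (1−p)³ + 3p(1−p)² × (1−p)³, that is, 0 of 3, or 1 of 3 followed by 0 of 3.

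- At p = 0.20: 0.512 + 0.384 × 0.512 = 0.7086, against the stated 71%.
- At p = 0.30, 0.40, 0.50 and 0.60: 49.43%, 30.93%, 17.19% and 8.24%, against 49, 31, 17 and 8%.

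The figures reproduce. The formula uses one DLT rate p for all 3 or 6 patients, so the rule presupposes that they share one dose.

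**By cohort against by dose.** This is an illustration; the SAP reports no DLT data. Assume that Cohort 5 has six patients, as 3.1 allows ("After a DLT has been identified the cohort will be expanded to 6 patients"), with one DLT patient at 8 mg/kg and a different one at 16 mg/kg.

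| Display | Count | Percent |
|---|---|---|
| Cohort 5 row | 2/6 | 33 |
| 8 mg/kg | 1/6 | 17 |
| 16 mg/kg, all six treated at both doses | 1/6 | 17 |
| 16 mg/kg, patient with the 8 mg/kg DLT not escalated | 1/5 | 20 |

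Read against 3.3, 2/6 meets the condition "de-escalating if 2 or more patients with DLTs are encountered", whereas 1/6 meets the condition for escalation. SAP 6.1 also contains the sentence "If a second DLT is reported this will be declared the MTD". Under that sentence, too, a row covering two doses does not identify which dose is meant. (That sentence and the definition quoted above from 6.1 do not agree with each other. This is a separate matter, and the passages must be reconciled.)

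**Modal rule within one cycle.** There are three injections per cycle (Days 1, 8 and 15, from 3.1). Assume that the event follows a 16 mg/kg injection, that all injections up to then were at 16 mg/kg, and that each later injection stays at 16, is reduced to 8 or is omitted. The reduced dose of 8 is an assumption for illustration.

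- Event after injection 1: 3 × 3 = 9 patterns. After injection 2: 3. After injection 3: 1. Total 13.
- Assigned to the lower dose: 16, 8, 8, which is 1 pattern.
- Tied, with no rule: 16, 8, omitted and 16, omitted, 8, which is 2 patterns.
- Assigned to 16 mg/kg, as they should be: 13 − 1 − 2 = 10, including 16, 16, 8.

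The patterns are not equally likely, so these counts are not a rate.

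**The case against.** The strongest reply is that the text already gives the right answer. SAP 6.1 commits to DLTs by dose level, 4.1 opens with treatment actually received, and 7.2.1 is only an index of titles. The shells are in a separate appendix and may divide Cohort 5 by dose. This stands as a limit: what is shown is that a title disagrees with the text, not that the dose will be missing from the finished table. A reader might infer that the MTD will be misreported; the document does not support that.

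On the modal rule, the stated purpose of occasional mistakes may be meant to exclude reductions after toxicity. Because the rule works cycle by cycle, it also separates Cohort 5's 8 and 16 mg/kg cycles. A reader might infer a 9-to-9 tie for a patient completing nine injections at each dose, but that needs a whole-study reading which the words do not bear. The rule also leaves a table by cohort untouched; it reaches only the two by-dose adverse event tables, and only after a reduction within a cycle. What remains is that 4.1 states neither an exception nor a tie rule.

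On listings, most DLTs are drug-related Grade 3 or 4 events (3.5) and so would appear in Listings 16.2.7-2.1 and 16.2.7-2.3. No title promises that they will be identified as DLTs or shown with the dose at onset. A DLT defined by inability to give the Cycle 1 schedule might not appear as an adverse event at all.

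Finally, recruitment closed early, and the SAP does not say that Cohort 5 was filled or expanded, or that any DLT occurred. That makes the illustration less likely. It does not remove the mismatch, because dose-escalation reporting is still planned.

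**Conclusion.** The point holds as an inconsistency in the reporting plan for the primary objective. The definition and the text of 6.1 work by dose level; the only listed DLT table works by cohort; and the two differ in Cohort 5. In the six-patient illustration the difference is 2/6 against 1/6 and 1/6 (or 1/5), which fall on opposite sides of the rule in 3.3 except that 1/5 is not a count the rule covers. This rests on the table title, since the shells cannot be seen.

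The modal-dose gap is secondary: one misassigned and two tied patterns out of 13 under the stated assumptions, confined to the by-dose adverse event tables.

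A reader might also infer that escalation decisions are compromised. They are not: the review committee works from patient safety data, not from these end-of-study tables. Nor does the point alter any sample size or error rate.

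**What to change.** 1. Present Table 14.2-1 by actual dose level within cohort, splitting Cohort 5 at the dose change. The denominator is the safety-set patients treated at that dose in that cohort, in line with section 6, which bases the primary objective on the safety set. Title 7.2.1 to match 6.1. Cohorts need not be pooled, since 3.3 gives readings only for 3 or 6 patients.
2. Attribute each DLT and treatment-emergent event to the actual dose last given before onset, and flag events that follow a mistaken dose.
3. In 4.1, limit the modal rule to occasional dosing mistakes in by-cycle summaries of data other than events, and add a tie rule.
4. Identify DLTs in a listing with cycle, dose at onset and dose history.

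If the shells already split Cohort 5 by dose, item 1 reduces to correcting the title.

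**Cost.** SAP wording, one restructured table, one listing and one derivation from dosing and onset dates; no new data. A patient can appear under more than one dose, so dose groups will not sum to N. A delayed toxicity that appears after a reduction counts at the reduced dose, which is why the dose history should be listed. No dosing or dose-reduction rule is proposed.
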